9.4.2 MISSING DATA

- PORT delay status (delay or timely PORT) will be considered 'delayed' for any evaluable patient with missing PORT delay status.
- TTP will be right-censored for evaluable patients who die prior to PORT initiation, are lost to follow-up prior to PORT initiation, or who haven't received PORT by the end of follow-up (18 weeks postoperatively).
- TPT will be right-censored for evaluable patients who die or are lost to follow-up prior to the conclusion of PORT, or who prematurely discontinue their intended course of PORT. TPT will also be right-censored for patients who have not completed PORT by the end of follow-up (18 weeks postoperatively).
- Time from surgery to PORT referral scheduling will be right-censored for evaluable patients who die prior to PORT initiation, are lost to follow-up prior to PORT initiation, or who haven't received PORT by the end of follow-up (18 weeks postoperatively).
- Time from surgery to appointment with radiation oncology will be right-censored for evaluable patients who die prior to PORT initiation, are lost to follow-up prior to PORT initiation, or who haven't received PORT by the end of follow-up (18 weeks postoperatively).

- Analyses of exploratory endpoints will be conducted using complete case analysis.

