To evaluate the preliminary clinical impact of NDURE compared with UC on delays starting PORT among white and AA HNSCC patients.	PORT delay, defined per National Comprehensive Cancer Network Guidelines as the initiation of PORT > 6 weeks (42 days) following definitive surgery for HNSCC.
Secondary	
To evaluate the preliminary clinical impact of NDURE compared with UC on time-to-PORT among white and AA HNSCC patients.	Time-to-PORT initiation, defined as the number of days from the date of definitive surgery for HNSCC to the date of initiation of PORT. Treatment package time, defined as the number of days from the date of definitive surgery for HNSCC to the date of PORT completion.
To evaluate the preliminary clinical impact of NDURE compared with UC on racial disparities in delays starting PORT among white and AA HNSCC patients.	PORT delay, defined per National Comprehensive Cancer Network Guidelines as the initiation of PORT > 6 weeks (42 days) following definitive surgery for HNSCC. Time-to-PORT initiation, defined as the number of days from the date of definitive surgery for HNSCC to the date of initiation of PORT.

Table 2. Study Objectives and Endpoints

	Treatment package time, defined as the number of days from the date of definitive surgery for HNSCC to the date of PORT completion.
To evaluate the preliminary impact of NDURE compared with UC on cancer care delivery processes.	Pre-surgical radiation consultation, defined as the attendance by the patient at a consultation with the treating radiation oncologist prior to surgery to discuss radiation therapy in the definitive or adjuvant setting.
	Pre-RT dental extractions, defined as the extraction of indicated carious/non-restorable teeth prior to or during definitive surgery.
	Time from surgery to PORT referral, defined as the time, in days, from the date of the definitive surgical procedure to the date the referral (or postoperative appointment) is placed to discuss adjuvant therapy with the treating radiation oncologist.
	Time from surgery to postoperative appointment with radiation oncology, defined as the time, in days, from the date of the definitive surgical procedure to the date that the patient attends a postoperative appointment with radiation oncology
Exploratory	

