4.2.4 END-OF-STUDY DEFINITION

Patients will be followed for collection of primary (PORT delay) and secondary (e.g., TTP, PORT duration, and treatment package time) for one year (365 days) from the date of surgery.

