3. Have an indication for PORT per NCCN Guidelines based on the presence of at least one of the following adverse features on final pathologic evaluation: ENE, positive margin, pT3 or pT4 primary, at least pN1 nodal disease (per AJCC 8th edition for p16-ve non-oropharyngeal SCC or AJCC 7th edition for p16+ve oropharyngeal SCC), nodal disease in levels IV or V, PNI or LVI

Analysis will be performed based on assignment at randomization regardless of the intervention received (modified intent to treat). This analysis set will be used for analysis of the secondary endpoint TTP.

The **treatment package time (TPT) analysis set** is the TTP analysis set restricted to patients who have initiated PORT.

The **full analysis set (FAS)** is the set of all trial participants who enroll and are eligible for the study. Patients who enroll but subsequently drop out prior to receiving any of the assigned intervention will be replaced. The FAS will be used for evaluation of the pre-surgical radiation consultation, and for secondary analyses of both the primary endpoint and secondary endpoints.

The **dental evaluation prior to surgery analysis set** will be the FAS restricted to patients who receive curative intent surgery at MUSC and are indicated for dental evaluation.

The **extraction of indicated teeth analysis set** is the subset of patients in the dental evaluation prior to surgery analysis set who are indicated for dental extractions prior to surgery.

The **time from surgery to PORT referral scheduling analysis set** and **time from surgery to appointment with radiation oncology analysis set** are equivalent to the TTP analysis set.

The **Per protocol set** is composed of all patients enrolled in the trial who have completed all 3 of the ENDURE intervention sessions as described in the protocol. This analysis set will be used for secondary analyses of both the primary endpoint and secondary endpoints.

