Treatment package time, NDURE vs UC: TPT is defined as the number of days between the date of definitive surgery and the date of PORT completion. Analysis will be conducted using cumulative incidence plots (1 – Kaplan-Meier plots) with Greenwood variance estimation to construct corresponding 90% CIs. Treatment group comparisons will be conducted using a stratified log-rank test adjusting for randomization stratification variables. TPT will be right-censored as described in Section 9.4.2. The hazard ratio comparing the two arms will be estimated using Cox proportional hazards regression controlling for stratification variables. A sensitivity analysis will be conducted treating deaths after PORT initiation but prior to the completion of PORT as a competing risk to evaluate the bias incurred in cumulative incidence estimation by right-censoring deaths. Analyses will be performed using the TPT analysis set.

Treatment package time (Black vs White) in NDURE vs UC: TPT cumulative incidence plots (1 – Kaplan-Meier plots) will be constructed for Black and White patients randomized to NDURE and for Black and White patients randomized to UC as described. Group comparisons will be conducted using a stratified log-rank test, but controlling only for predicted radiation facility as a randomization stratification variable since a race-by-trial arm interaction term is used to evaluate this hypothesis. A Cox proportional hazards regression model will be fit as described with appropriate race-by-trial arm interaction. Censoring rules will be as described in Section 9.4.2. A sensitivity analysis will be performed treating deaths after PORT initiation but prior to the completion of PORT as a competing risk. Analyses will be conducted using the TPT analysis set.

Time from surgery to PORT referral scheduling, NDURE vs UC: Time from surgery to PORT referral scheduling will be analyzed using the approach described for all time-to-event endpoints. Censoring rules will be as described in Section 9.4.2. Analyses will be performed using the time from surgery to PORT referral scheduling analysis set.

Time from surgery to appointment with radiation oncology, NDURE vs UC: Time from surgery to appointment with radiation oncology will be analyzed using the approach described for all time-to-event endpoints. Censoring rules will be as described in Section 9.4.2. Analyses will be performed using the time from surgery to appointment with radiation oncology analysis set.

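### The 1 − Kaplan-Meier curves for treatment package time overstate PORT completion, because patients who stop early are censored and the competing-risk check covers deaths only

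*Combined protocol and SAP*

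**What the plan says.** Table 2 (Section 3) makes TPT a secondary endpoint: "Treatment package time, defined as the number of days from the date of definitive surgery for HNSCC to the date of PORT completion". The event is therefore completion of the course. Section 9.3 takes the TTP analysis set and keeps those in it who began PORT: "restricted to patients who have initiated PORT".

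Section 9.4.2 sets the censoring rules. "TPT will be right-censored for evaluable patients who die or are lost to follow-up prior to the conclusion of PORT", and the same sentence adds those "or who prematurely discontinue their intended course of PORT". A separate sentence covers patients still short of completion at the cut-off: "TPT will also be right-censored for patients who have not completed PORT by the end of follow-up (18 weeks postoperatively"). No censoring date is stated for those who stop early. Section 4.2.4 says that outcomes, TPT among them, are followed "for one year (365 days) from the date of surgery".

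Section 9.4.4.2 gives the estimator: "Analysis will be conducted using cumulative incidence plots (1 – Kaplan-Meier plots) with Greenwood variance estimation". A stratified log-rank test and a Cox model follow. The one sensitivity analysis consists of "treating deaths after PORT initiation but prior to the completion of PORT as a competing risk". The Black versus White TPT analysis follows the same pattern.

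Receipt of the planned total dose is a separate exploratory endpoint (Table 2; Section 8.4.6), compared between arms under Section 9.4.9 on complete cases (Section 9.4.2). Planned and delivered dose are both collected (Section 8.3).

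**The concern.** Censoring is harmless to a Kaplan-Meier curve when the censored patient could still have the event later, at the same rate as those who remain. Loss to follow-up may fit that description. Permanent discontinuation does not, because it rules the event out. When such patients are censored, their share of the probability is reassigned to patients still on treatment, and 1 − Kaplan-Meier no longer estimates the proportion who complete.

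The plan accepts this argument for deaths and adds an analysis to gauge that bias. It does not do so for early stopping. Even in the death analysis, stoppers remain censored.

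At stake is how TPT is read. It is the only secondary endpoint that covers the end of radiotherapy. A reader who sees both arms' curves rise to nearly 100% would conclude that almost everyone who started PORT finished it, whatever actually happened.

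**Working it through.** **The plan's own figure.** No power or expected rate is given for TPT. The only power figure for the RCT is 83%, for the primary endpoint (Section 9.2.2: 75 per arm, 45% versus 25%, two-sided α = 0.10, pooled Z-test). It reproduces:

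- Null SE = √(2 × 0.35 × 0.65 / 75) = 0.0779
- Alternative SE = √((0.45 × 0.55 + 0.25 × 0.75) / 75) = 0.0762
- Power = Φ((0.20 − 1.645 × 0.0779) / 0.0762) = Φ(0.94) ≈ 83%

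This figure does not depend on the TPT rule.

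**Why the curve goes to 100%.** The Kaplan-Meier estimate is the product of (1 − 1/r) over completion times, where r is the number still at risk. If the last patient at risk completes before the cut-off, the final factor is 1 − 1/1 = 0, so 1 − KM = 100% however many were censored before.

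Take 20 starters of whom 2 stop before anyone completes:

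- Stoppers censored: S = (17/18)(16/17)…(0/1) = 0, so 1 − KM = 100%.
- Stopping as a competing event (Aalen-Johansen): probability of being free of any event after the two stops = (19/20)(18/19) = 0.90. Each of the 18 completions then adds 0.90/18 = 0.05, and 18 × 0.05 = 90%.
- Observed proportion completing: 18/20 = 90%.

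**Size on a realistic time scale.** All rates and timings here are assumptions. PORT start is Normal with mean 40 and SD 8 days, the course lasts 42–49 days, stopping is uniform over the course, stoppers are censored at the stop date, and the cut-off is day 126.

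| Assumed early-stop rate | 1 − KM, day 126 | Cumulative incidence, day 126 | Overstatement |
|---|---|---|---|
| 2% | 100% | 98% | 2 points |
| 5% | 100% | 95% | 5 points |
| 10% | 100% | 90% | 10 points |
| 15% | 100% | 85% | 15 points |

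At day 100 with 10% stopping, the curve reads about 96% against about 87%. With a start of mean 42 and SD 10 days and a course of mean 44 and SD 4 days, the day-126 figures are the same to the nearest point. The day-100 figures at 10% stopping become about 90% against 81%.

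**Between-arm test.** Assumptions: 70 per arm, the second set of timings in both arms, 5% stopping in usual care, unstratified log-rank, two-sided 0.10, 2,000 trials per scenario. The entries are the chance of a significant result against NDURE.

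| Stopping in NDURE | Stoppers censored | Stoppers kept at risk to day 126 | Comparison of completion proportions |
|---|---|---|---|
| 5% (equal) | 5% | 5% | 6% |
| 10% | 7% | 23% | 32% |
| 15% | 7% | 50% | 66% |
| 20% | 8% | 75% | 89% |
| 25% | 9% | 91% | 98% |

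The censored test stays close to its 5% one-tail null rate throughout. If NDURE patients also start PORT 4 days earlier and 20% versus 5% stop, the censored test favours NDURE in 53% of trials (approximate hazard ratio for completion 1.39). With stoppers kept at risk it favours NDURE in 0.4% and usual care in 31% (approximate subdistribution hazard ratio 0.81).

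**The case against.** The defence has five parts.

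1. A reader might infer that the plan hides the harm TPT was added to detect. The documents do not support that. The amendment history (Section 10.4, version 6.0) names unintended breaks as the concern. A break that lengthens a completed course still lengthens TPT and is counted. Only permanent stops drop out. This stands.

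2. Permanent stopping is measured elsewhere. The completion endpoint was added in the same amendment and is compared between arms. In the table above it detects excess stopping better than a competing-event TPT test. This also stands, with the limit that it is exploratory and complete-case. PORT duration does not fill the gap, because it covers completers only.

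3. A reader might infer that the whole TPT analysis is invalid. It is not. Log-rank and Cox with competing events censored compare the cause-specific hazard of completion, that is, pace among patients still on treatment. That is a recognised estimand. The result with the 4-day earlier start is not an error of that test, which answers a different question from who completes. Preferring a subdistribution hazard ratio is a choice of estimand, not a correction.

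4. Section 9.4.2 gives no censoring date. If stoppers were carried to day 126 and censored there, 1 − KM would equal the true proportion completing. This does not rescue the text: the 18-week cut-off appears as a separate rule, so the stop date is the natural reading. It does mean that the date must be written down.

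5. The size rests on assumed rates. At 2% stopping the gap is about 2 points at day 126 and about 1 point near the median. With equal rates in both arms the log-rank is not materially biased. With a longer tail of late starters (again an assumption) the curve reaches about 97% rather than 100%, though a gap remains.

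**Conclusion.** The concern holds for the 1 − Kaplan-Meier curves, overall and in the Black versus White analysis. As written, they do not estimate the cumulative incidence of PORT completion, and no planned analysis examines the part of the bias due to discontinuation. Provided stoppers are censored at the stop date, the overstatement at day 126 is about the early-stop rate: 2 to 15 points for assumed rates of 2 to 15%. The true rate is not in the documents.

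The log-rank and Cox results stand as cause-specific comparisons, but they should not be read as evidence that completion is similar between arms. They had only a 7–9% chance of signalling stopping rates of 10–25% against 5%. The documents support neither a claim that early stopping is invisible to the trial nor one that the hazard ratio is wrong. The size and direction of any difference between arms remain unknown until stopping rates are observed.

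**What to change.** In Sections 9.4.2 and 9.4.4.2:

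- Estimate the TPT cumulative incidence curves (overall and Black versus White) with premature discontinuation and death both as competing events, using the Aalen-Johansen estimator. At minimum, extend the existing competing-risk sensitivity analysis from deaths to discontinuation.
- State the TPT censoring date for each reason. In doing so, reconcile the 18-week end of TPT follow-up in Section 9.4.2 with the 365 days in Section 4.2.4.
- Label the Cox hazard ratio as cause-specific. A subdistribution hazard ratio may be added as supportive.
- Report the proportion completing the intended course, by arm, beside the TPT results.

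The cost is a few sentences of SAP text and a standard procedure. Planned and delivered dose, already collected, identify the stoppers. The date of last treatment for a stopper is not a separate item in Section 8.3, so the team should confirm that it is recorded. The design and sample size do not change.

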
^a Study Visit 5 assessments are to be administered after the start of PORT. For the purposes of determining when to administer Study Visit 5 assessments, the study coordinator will determine that a patient has started PORT either by verifying in the EMR (for patients undergoing PORT at MUSC) or by contacting the patient no sooner than 8 weeks after surgery (for patients undergoing PORT outside of MUSC). If PORT is indicated but never initiated, Study Visit 5 assessments are to be completed 12 weeks after surgery.
 
^b Following completion of PORT, the study coordinator will gather all of the required source documentation to ascertain efficacy and cancer care delivery endpoints as well as adjuvant therapy details
							

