As a result of the aforementioned three strategies, retention of subjects is expected to be highly feasible. The scheduled timepoints of navigator-participant interaction (initial surgical consultation, prior to hospital discharge, first clinic visit after hospital discharge) were chosen because these are situations in which the likelihood of contact is ~100%. Although challenges with retention for cancer studies due to mortality (overall and disease-specific) and treatment toxicity are potentially problematic, we do not think that they will limit retention in this feasibility study of NDURE. The rate of on-treatment mortality (during surgery or adjuvant therapy) is quite low (<5%) and the study follow-up does not extend past the completion of therapy. Thus, lack of retention due to mortality is not expected to be significant. Treatment toxicity is potentially a problem, as patients may not want to answer surveys while undergoing treatment or choose to withdraw due to competing treatment demands. We do not expect this to be a problem, however, because NDURE will be integrated into routine clinical care and thus should not create an excess time burden for patients. In fact, it is likely that participation in the intervention, which is expected to improve care coordination and decrease barriers to care, will make this potential source of dropout less likely than other intervention trials. Using NDURE to address individualized barriers to timely HNSCC treatment is a significant strength and innovation of the study and will likely also improve retention relative to historical rates.

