8.4.6 CANCER CARE DELIVERY PROCESS ASSESSMENTS

A Cancer Care Delivery Process form is included as the eCRF and will be completed by the program coordinator using information from the EMR.

Pre-Surgical Radiation Consultation is defined as the attendance by the patient at a consultation with the treating radiation oncologist (at MUSC or elsewhere) prior to surgery to discuss RT in the definitive or adjuvant setting. Patients who see a radiation oncologist at one facility prior to surgery but receive PORT at a different facility are evaluated as 'no' for this measure.

Pre-Radiation Therapy Dental Evaluation is defined as the evaluation by a dentist for pre-radiation dental extractions. Edentulous patients are non-evaluable for this measure. Dentulous patients who do not have a pre-surgical dental evaluation are evaluated as 'no'.

Pre-Radiation Extractions of Indicated Teeth with Definitive Surgery is defined as the extraction of indicated carious/non-restorable teeth either prior to or during definitive surgery. Patients who have a dental evaluation that indicates the need for extractions, but for whom teeth are not extracted prior to or during

surgery are evaluated as 'no' for this measure. Edentulous patients and dentulous patients who have a dental evaluation and extractions are not recommended are not evaluable for this measure.

Time from Surgery to Pathology Report is defined as the production of the pathology report from the definitive surgical procedure within the EMR. Addenda to the pathology report at the request of the HNSCC team (e.g. tumor p16 status) are not counted in this measure.

Time from Surgery to PORT Referral is defined as the time, in days, from the date of the definitive surgical procedure to the date the referral (or postoperative appointment) is placed to discuss adjuvant therapy with the treating radiation oncologist. For patients who have seen a radiation oncologist prior to surgery, this metric refers to the scheduling of the post-operative follow-up appointment with the radiation oncologist. In situations in which a patient is re-referred postoperatively (i.e., a patient is referred to a radiation oncologist at one facility and then decides to get treatment at a different facility), the measure is evaluated using the time to the second referral.

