Time from Surgery to Postoperative Appointment with Radiation Oncology is defined as the time, in days, from the date of definitive surgery to the date that the patient attends a postoperative appointment with radiation oncology. For patients who have seen a radiation oncologist prior to surgery, this measure refers to the scheduling of the post-operative follow-up appointment with the radiation oncologist. In situations in which a patient is re-referred postoperatively (i.e., a patient is referred to a radiation oncologist at one facility and then decides to get treatment at a different facility), the measure is evaluated using the time to the second referral. In situations in which an appointment is scheduled but the patient does not attend the appointment, the measure is evaluated using the date for which the appointment was actually attended.

PORT Duration, defined as the number of days from the initiation of PORT to the completion of PORT among patients who complete the intended course of adjuvant therapy.

Completion of intended course of PORT, defined as receipt of the planned PORT dose (total Gy).

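### Section 9.4.2 censors time to PORT referral and time to radiation oncology appointment on PORT initiation rather than on the referral or visit; its 18-week cut for treatment package time also conflicts with 365-day follow-up

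*Combined protocol and SAP*

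**What the plan says.** **Censoring rules.** Section 9.4.2 states: "Time from surgery to PORT referral scheduling will be right-censored for evaluable patients who die prior to PORT initiation". The sentence continues with two further conditions: loss to follow-up before PORT starts, and no PORT by 18 weeks. The rule for the second process endpoint has the same form: "Time from surgery to appointment with radiation oncology will be right-censored for evaluable patients who die prior to PORT initiation".

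**Event definitions.** Section 8.4.6 sets the events differently. "Time from Surgery to PORT Referral is defined as the time, in days, from the date of the definitive surgical procedure" to the day the referral or postoperative appointment is placed. The appointment endpoint runs "from the date of definitive surgery to the date that the patient attends a postoperative appointment with radiation oncology".

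**Who is analysed.** Section 9.3 says that the two analysis sets "are equivalent to the TTP analysis set". That set requires randomization, surgery at the study site and a pathologic indication for PORT. It does not require PORT to start.

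**Link between the sections.** For each of these endpoints Section 9.4.4.2 says that it "will be analyzed using the approach described for all time-to-event endpoints. Censoring rules will be as described in Section 9.4.2". It makes no exception.

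**Treatment package time (TPT).** Section 9.4.2 also censors TPT at 18 weeks and describes that point as the end of follow-up. Section 4.2.4 follows patients for TPT for 365 days from surgery. Section 8.4.4 gives the 126-day limit for time-to-PORT (TTP) only.

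**The concern.** The censoring condition names the wrong event. Referral and the radiation oncology visit normally come before PORT, so a patient can have both dates recorded and still never start PORT. The protocol expects such patients: "If PORT is indicated but never initiated, Study Visit 5 assessments are to be completed 12 weeks after surgery". Followed as written, 9.4.2 turns their observed events into censored observations. It also gives no date at which to censor them.

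Scheduling these appointments is a core part of the NDURE intervention (Section 6.1.1.1), so the two endpoints show whether the intervention changed the processes it targets. If more patients in one arm never start PORT, the literal rule makes referral look slower in that arm even when referral times are the same. A difference in starting PORT would then be read as a difference in referral. If the shares are equal, the test keeps its level but both curves are too low.

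For TPT, some completions that fall within the year of follow-up would not count as events. Patients who start PORT after day 126 would enter the TPT set but be censored before their PORT begins.

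**Working it through.** **1. One patient under both texts.** Take a patient referred on day 8 and seen on day 15 who never starts PORT.
- Section 8.4.6: referral time 8 days and appointment time 15 days, both observed.
- Section 9.4.2 as written: no PORT by 18 weeks, so both are censored, at an unstated date.
- Sections 9.3 and 9.4.4.2: the patient is in both analysis sets, and nothing overrides 9.4.2.

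In the same section, the TPT rule ties censoring to the end of PORT, which is TPT's own event. The two process endpoints instead carry the TTP wording.

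**2. Sample size used below.** Section 9.2.2 gives 75 per arm, 45% versus 25%, two-sided alpha 0.10 and 83% power. With a pooled-variance Z-test:
- null SE = sqrt(2 × 0.35 × 0.65 / 75) = 0.0779
- alternative SE = sqrt((0.45 × 0.55 + 0.25 × 0.75) / 75) = 0.0762
- power = Φ((0.20 − 1.645 × 0.0779) / 0.0762) = Φ(0.94) = 82.7%

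This reproduces the stated figure. The concern does not depend on it; it only supplies n = 75.

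**3. Effect on the curve.** If everyone is referred and k of 75 never-starters are censored at day 126, the 18-week Kaplan-Meier estimate is 1 − k/75. Each such patient costs 1/75 = 1.3 points. More generally, with never-start share f, the estimate at day t is (1 − f) × F(t), where F(t) is the true cumulative incidence of referral. Assuming gamma referral times (shape 4, mean 16 days), F(30) is about 94%, and the estimate falls to 90%, 85% and 80% for f = 5%, 10% and 15%. If never-starters are censored on their referral day instead, it is 93%, 92% and 91%.

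**4. Effect on the test.** The documents give no never-start rate, so the shares are assumed. The simulation used:
- 75 per arm, with 25 AA and 50 white patients in each
- a 50/50 split by predicted facility (assumed)
- the same referral-time distribution in both arms (gamma, shape 4, mean 12 days, rounded up), with everyone referred
- a log-rank test stratified by race and facility
- 2,000 trials per scenario, except 1,000 for the two small-gap rows; Monte Carlo SE about 0.7 to 1.1 points

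The table shows false rejections at nominal 10%, with nominal 5% in brackets. Both levels are given because Section 9.4.1 pairs p = 0.05 with 90% confidence intervals.

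| Never start PORT, NDURE / UC | Censored at day 126 | Censored at referral day |
|---|---|---|
| 3% / 3% | 9% (4%) | 9% (4%) |
| 10% / 10% | 10% (5%) | 11% (6%) |
| 2% / 4% | 12% (7%) | 11% (6%) |
| 3% / 5% | 11% (5%) | 11% (5%) |
| 3% / 8% | 23% (14%) | 13% (6%) |
| 5% / 10% | 20% (12%) | 11% (6%) |
| 5% / 15% | 46% (34%) | 19% (11%) |

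Counting the referral as the event gives 10-11% (5-6%). Censoring at a uniform time between referral and day 126 gives 22%, 20% and 44% at nominal 10% for the last three rows. For 5% / 15% with day-126 censoring, the mean 18-week estimates are 94.9% and 85.3%; the truth is 100% in both arms.

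**5. TPT.** Eighteen weeks is 126 days, and 365 − 126 = 239 days of follow-up go unused. Assume a 6-week course, a length that appears only in the travel-support text of Section 6.1.1.1. A start after day 126 − 42 = 84 then cannot become an event. Fit a lognormal TTP to P(T > 42) = 45% (UC) and 25% (NDURE), with assumed log-SD s. Then P(T > 84) = 1 − Φ(z + ln 2 / s), with z = 0.126 for UC and 0.674 for NDURE:

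| s | UC | NDURE |
|---|---|---|
| 0.25 | 0.19% (0.1 of 75) | 0.03% (0.0 of 75) |
| 0.35 | 1.76% (1.3 of 75) | 0.40% (0.3 of 75) |
| 0.45 | 4.79% (3.6 of 75) | 1.34% (1.0 of 75) |

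Starts after day 126 are at most 0.5% in either arm.

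**The case against.** The best defence is that nobody would code it this way. Section 9.4.2 is headed as a missing-data section, and a patient with a recorded referral date has nothing missing for that endpoint. Right-censoring ordinarily means that the event was not seen. The wording was most likely carried over from the TTP rule, and a programmer would probably use the observed date. That is a fair forecast of practice, but it does not repair the text. The rule does state a condition, and the condition refers to the wrong event. Two analysts could follow the plan in good faith and get different results.

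The second objection concerns size, and much of it stands. Material inflation needs three things together: the literal reading, censoring well after referral, and a between-arm gap clearly above 2 points. The 5% / 15% row should not be taken as expected. The on-treatment mortality below 5% in Section 5.5 (under 4 of 75) does not settle the share either, because it includes deaths after PORT starts and leaves out living patients who never start. If some never-starters were truly never referred, censoring them is right and the inflation shrinks.

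On TPT, Section 4.2.4 lists TTP under the same 365 days, yet Section 8.4.4 cuts TTP at day 126. Collecting data for a year and analysing to 18 weeks is therefore not in itself a contradiction. An analyst would know to cut TPT at 18 weeks, and a fixed cut does not bias estimates before it. What remains is that 9.4.2 calls 18 weeks the end of follow-up, which for TPT it is not, and gives no reason for setting later completions aside.

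**Conclusion.** The concern holds. As written, the censoring rules for time to referral and time to appointment contradict the endpoint definitions, and they would discard observed events for patients who never start PORT or have not started by 18 weeks. The wording conflict is certain; the size of any bias is not. It depends on an unreported never-start share, on the gap between arms, and on a censoring date that 9.4.2 does not supply. It ranges from no effect on the test with equal shares to roughly a doubling of the nominal 10% error for 5-point gaps with day-126 censoring. The TPT conflict is real but lesser: between 0.0 and 3.6 of 75 patients per arm under the stated assumptions. The primary endpoint, its power and the sample size are unaffected. It should be corrected before the analysis.

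**What to change.** In Section 9.4.2, replace the two process-endpoint rules with wording such as:

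> Referral (or the attended appointment) counts as an event on the date it occurs, whether or not PORT is later started. A patient without that event is censored at the earliest of death, loss to follow-up or 18 weeks after surgery.

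For TPT, reconcile 9.4.2 with 4.2.4. Either count completions seen within the 365 days as events, or state that 18 weeks is a chosen analysis horizon, with the reason, and stop describing it as the end of follow-up.

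The cost is a few sentences and a few lines of programming. The dates needed are already collected under the Schedule of Activities, and neither trial conduct nor sample size changes.
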